**Document History – Changes compared to previous final version of SAP**

| Date        | Time point       | Reason for update  | Outcome for update   | Section and title impacted (Current)  |
|-------------|------------------|--|--|---|
| 02-Nov-2022 | Prior to DB lock | Creation of final version  | N/A - First version  | NA  |
| 06-Aug-2024 | Prior to DB lock | Updates  | Detailed baseline characteristics that will be included in the output table are included in the SAP  | Section 2.3.2   |
| 06-Aug-2024 | Prior to DB lock | The decision of the early termination of the study                                     | 
The following analyses will not be performed, therefore removed from the SAP:
 

1. The pooling of the placebos from different cohorts

2. All sensitivity and supplemental analyses for the primary endpoint will not be performed, therefore removed from the SAP.

3. All the analyses on exploratory objectives and endpoints stated in Section 1.2 will not be performed, therefore removed from the SAP.

4. Planned Interim Analyses

 | Sections 2.1, 2.5.3, 2.5.4, 2.5.5, 2.5.6, 2.6.1.1, 2.6.1.2, 2.6.1.3, 2.8, 2.9, 2.11, 2.12, 2.13 |
| 12-Nov-2024 | Prior to DB lock | Updates  | Clarified previously unclear or inconsistent protocol languages  | Section 2   |
| 12-Nov-2024 | Prior to DB lock | Specify “On-treatment period” and “Treatment emergent AE”                              | The last treatment plus 30 days defined as on-treatment period and will be used as the time frame of “Treatment emergent AE”   | Section 2.1.1   |
| 12-Nov-2024 | Prior to DB lock | Update Protocol deviation codes exclusion of analysis sets                             | Detailed Protocol deviation codes provided for exclusion of analysis sets  | Table 2-1   |
| 12-Nov-2024 | Prior to DB lock | Consistency to the updated protocol for GAP score                                      | GAP score will not be presented as a baseline characteristics due to lacking of the data   | Section 2.3   |
| 12-Nov-2024 | Prior to DB lock | Add “Direction of interest for worst case value” for biochemistry and hematology tests | Two tables added accordingly   | Section 5.3   |
| 12-Nov-2024 | Prior to DB lock | To be consistent using terminology   | Change “Background therapy” into “standard of care”  | Throughout  |
|             |                  | Details in Progression-free survival (PFS) events                                      | Non-elective respiratory hospitalizations defined  | Section 2.6.1.1   |

## List of abbreviations

|        |  |
|--------|--|
| AE     | Adverse Event  |
| ANOVA  | Analysis of Variance                                 |
| ATC    | Anatomical Therapeutic Chemical                      |
| AUC    | Area Under the Curve                                 |
| AWT    | Airway Measures                                      |
| CRF    | Case Report Form                                     |
| CSR    | Clinical Study Report                                |
| CTCAE  | Common Terminology Criteria for Adverse Events       |
| CV     | Coefficient of Variation                             |
| DBL    | Database Lock  |
| DMC    | Data Monitoring Committee                            |
| DMS    | Document Management System                           |
| EoT    | End of Treatment                                     |
| CCI    | [REDACTED]   |
| FVC    | Forced Vital Capacity                                |
| FVC%p  | Forced Vital Capacity expressed in percent predicted |
| IA     | Interim Analyses                                     |
| IPF    | Idiopathic Pulmonary Fibrosis                        |
| LLOQ   | Lower Limit of Quantitation                          |
| MedDRA | Medical Dictionary for Drug Regulatory Affairs       |
| MMRM   | Mixed Effect Model for Repeated Measurement          |
| PD     | Pharmacodynamic                                      |
| PFS    | Progression-free Survival                            |
| PK     | Pharmacokinetics                                     |
| PRO    | Patient-reported Outcomes                            |
| PT     | Preferred Term                                       |
| qGG    | Quantitative Ground-glass                            |
| qHC    | Quantitative Honeycombing                            |
| qHRCT  | Quantitative High-resolution Computed Tomography     |
| qILD   | Quantitative Interstitial Lung Disease               |
| qLF    | Quantitative Lung Fibrosis                           |
| SAP    | Statistical Analysis Plan                            |
| SAS    | Statistical Analysis System                          |
| SD     | Standard Deviation                                   |
| SMQ    | Standardized MedDRA Query                            |
| TFLs   | Tables, Figures, Listings                            |
| TP     | Trial Programmer                                     |
| TS     | Trial Statistician                                   |
| ULOQ   | Upper Limit of Quantitation                          |

## 1 Introduction

This Statistical Analysis Plan (SAP) is to describe the implementation of the statistical analysis planned in the protocol (Version 05). The SAP contains detailed information to aid the production of statistics & programming input into the Clinical Study Report (CSR) for trial “CADPT09A12201”.

### 1.1 Study design

[figure not shown]
This is a randomized, placebo-controlled, participant- and investigator-blinded platform study in participants with IPF.

This study uses a platform type design to investigate “multiple targeted therapies in the context of a single disease in a perpetual manner” (Woodcock and LaVange 2017). Each investigational product and matching placebo entered the trial at a given time will be considered a unique cohort. The decision to include future cohorts is not dependent on performance of prior investigational products or cohorts. Each time a new cohort is introduced, investigational product specific information will be added to the protocol (Protocol Section 17) as a substantial amendment and submitted to Health Authorities and Ethical Committees, as required by local regulations. The cohort specific analysis will be added into an SAP amendment accordingly where necessary.

If multiple cohorts are open, participants will be allocated based on the cohort-specific eligibility criteria. Should a participant be eligible for more than one cohort, they will be randomized to any suitable cohort.

For each completed cohort, the data analysis will be performed upon final database lock for the cohort, and the results will be reported upon completion of each cohort in an end of cohort report. In general, each cohort in the study will undergo similar study evaluations and assessments. Each cohort will include a screening period (Day -42 to Day -1), a treatment period of 26 weeks (Day 1 to Day 183), and a post treatment safety follow-up that is cohort specific per Protocol Section 17.

**Figure 1-1 Study design**

R = Randomization

## 1.2 Study objectives, endpoints and estimands

**Table 1-1 Objectives and related endpoints**

| Objective(s)   | Endpoint(s)  |
|--|--|
| Primary objective(s)  | Endpoint(s) for primary objective(s)  |
| 

To assess the efficacy of the investigational products compared to placebo in participants with IPF

  | 

Change from baseline to end of treatment epoch (26 weeks of treatment) in Forced Vital Capacity (FVC) expressed in percent predicted

   |
| Secondary objective(s)  | Endpoint(s) for secondary objective(s)  |
| 

To assess the efficacy of the investigational products, compared to placebo in participants with IPF

To assess the impact of the investigational products on "progression-free survival (PFS)"

To assess the incidence of absolute decline in FVC <math>\geq 10\%</math> predicted

To assess the impact of the investigational products on pulmonary physiology

To assess the impact of the investigational products on exercise capacity

To assess the impact of the investigational products on patient reported outcome

To assess the safety and tolerability of the investigational products in participants with mild to moderate IPF

 | 

Change from baseline to end of treatment epoch (26 weeks of treatment) in Forced Vital Capacity (FVC) expressed in mL

Time to progression as defined by a composite endpoint including any of the following events:

Absolute reduction from baseline of <math>\geq 10\%</math> predicted in FVC

Nonelective hospitalization for respiratory events

Lung Transplant

Death

Number of participants with absolute decline of <math>\geq 10\%</math> predicted in FVC

Change from baseline to the end of treatment epoch (26 weeks of treatment) in DLCO absolute and percent predicted

Change from baseline to the end of treatment epoch (26 weeks of treatment) in 6-minute walk distance

Change from baseline to the end of treatment epoch (26 weeks of treatment) in scores from the L-IPF (Impacts and Symptoms Modules), K-BILD, Leicester cough, and R-Scale for PF questionnaires

Adverse Events, physical examinations, labs, ECGs, vital signs

 |
| Exploratory objective(s)  | Endpoint(s) for exploratory objective(s)  |
| 

To assess the impact of the investigational products on disease exacerbation.

To assess the impact of the investigational products on additional "progression-free survival (PFS)" analysis

To evaluate change in extent of pulmonary fibrosis quantified by HRCT scan

To explore the impact of the investigational products on peripheral blood biomarkers

  | 

IPF exacerbations or suspected exacerbations as determined by investigator and by using modified diagnostic criteria derived from Collard et al 2016 and exacerbations as determined by the investigator as AEs/SAEs

Time to progression as defined by a composite endpoint including any of the following events:

Absolute reduction from baseline of <math>\geq 5\%</math> predicted in FVC

Non-elective hospitalization for respiratory events

Lung Transplant or Death

Change in fibrosis from baseline to the end of treatment epoch (26 weeks of treatment) in quantitative high-resolution computed tomography (qHRCT)

Change from baseline in soluble pharmacodynamic, target engagement and disease markers (may include but are not limited to: cci [REDACTED] and additional protein profiling) in the peripheral blood.

  |

| Objective(s)  | Endpoint(s)   |
|---|---|
| 

The pharmacokinetics of the investigational products after multiple doses will be assessed.

To explore the pharmacogenetics for the potential disease association or participant stratification

CCI

 | 

Appropriate PK parameters will be calculated where possible using non-compartmental analysis. These may include Tmax, Cmax, AUCs. Population PK modelling may also be used for parameter estimation.

DNA analysis at baseline

 |
|   |   |
|   |   |

### 1.2.1 Primary estimand(s)

Estimands are not defined since this PIIa clinical trial is not intended for registrational purposes. Novartis is of the view that there will be only a few intercurrent events for this small non-registrational study. This SAP detailed sensitivity analyses to investigate the impact of the potential intercurrent events on the primary endpoint of interest, i.e., FVC%p, but will be omitted due to the decision of early termination of the study.

## 2 Statistical methods

A Clinical Study Report (CSR) will be prepared following the completion of the study. Any data analysis carried out independently by the investigator should be submitted to Novartis before publication or presentation.

### 2.1 Data analysis general information

The final CSR analysis will be performed by Novartis Trial Statistician (TS) and Trial Programmer (TP). SAS version 9.4 or higher (SAS Institute, Cary NC) or later software will be used to perform all data analyses and to generate tables, figures, and listings.

Novartis TS and TP will be performing the interim analyses including DMC planned and/or required analyses with separate SAP detailing the planned analysis.

Descriptive statistics on continuous data will include mean, standard deviation, median, 25th and 75th percentiles, minimum and maximum, while categorical data will be summarized as frequencies and percentages.

The cut-off date which data will be included in the analysis will be at the final Database Lock (DBL) date. All data will be considered in the analyses described hereafter.

There will be no center factor considered unless there is a strong evidence of data deviations from different centers. Planned stratification factor(s) will be included in the inferential statistical model as a covariate.

### 2.1.1 General definitions

**Investigational treatment** refers to any drug or combination of drugs or intervention administered to the study participants whose properties are being tested in the study.

The term '**date of first administration of study drug/treatment**' refers to the date on which the study drug/treatment was given for the first time for the participants in the cohort of the study.

The term '**date of last administration of study drug/treatment**' refers to the date on which the study drug/treatment was given for the last time in the cohort of the study.

The term '**study day**' refers to the Analysis Relative Day, Relative Start Day, or Relative End Day, as applicable. Day 1 is defined as the date of randomization.

For a particular date, study day will be calculated as follows:

- for dates on or after Day 1,

Study day = Assessment date – Day 1 +1

- for dates prior to Day 1,

Study day = Assessment date – Day 1.

The term '**baseline**' refers to the last assessment performed prior to the treatment. For spirometry data, baseline is considered as the assessment conducted in "Baseline" visit (Day 1), or the last assessment performed prior to the treatment when the assessment in the "Baseline" visit is missing.

The term '**on-treatment period**' is defined as the time between the first dose of study drug to 30 days after the last treatment visit (Day 183) if not missing or the date of last treatment visit attended in the study in case of drop-out or the death date if subject died in treatment epoch.

The term '**End of Treatment (EoT)**' refers to the last date of the on-treatment period as defined above.

The term '**treatment-emergent adverse event**' refers to any adverse event (AE) occurs in the "on-treatment period", started after the first dose of study treatment, or events present prior to the first dose of study treatment but increased in severity (based on preferred term (PT)).

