## **2.5 Analysis supporting primary objective(s)**

The primary aim of the study is to assess the efficacy of the investigational products, compared to placebo in IPF participants. This will be evaluated by assessing change from baseline to end of treatment epoch (26 weeks of treatment) in Forced Vital Capacity (FVC) expressed in percent predicted (FVC%p). Reduction of the decrease in change from baseline is considered a favorable outcome. The primary analysis will be conducted using PD analysis set.

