### **2.5.1 Primary endpoint(s)**

The primary endpoint of the study is change from baseline in FVC%p. It will be calculated as:

$FVC\%p \text{ (EoT)} - FVC\%p \text{ (Baseline)}$ .

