**Table 2-2 Composition of the robust weakly informative prior for the placebo tie slope**

|   | Comp1 | Comp2 | Comp3 |
|---|-------|-------|-------|
| W | 0.526 | 0.174 | 0.300 |
| M | -2.93 | -2.75 | -3.00 |
| S | 0.865 | 1.837 | 4.754 |

This effectively means that we assume a placebo decline of 3% at week 26 from the baseline for the placebo group is expected. This prior belief is fixed at the design stage. Any new placebo historical data that becomes available, will not be used as part of a prior. The impact of using this placebo prior means that there would be in effect 11 more placebo participants contributing to the data analysis. A non-informative prior will be used for the rest of the parameters, assuming the change from baseline in FVC%p has a normal distribution with mean=0 and a very large SD (e.g., 1E6).

The primary summary measure of interest is the difference in FVC%p between active and placebo at week 26 derived from the Bayesian statistical model as the posterior mean estimation of the treatment effect over placebo for change from baseline FVC %p at the end of treatment (26 weeks). Statistical evidence of treatment effect will be concluded if the probability that the effect is better than placebo by 90% and there is at least 50% probability that the effect over placebo is >1.3%. No adjustments for multiplicity will be applied for this exploratory study.

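### The SAP ties end of treatment and the treatment-emergent window to 30 days after the Day 183 visit, which misdates the primary endpoint formula and conflicts with its other safety windows

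*SAP*

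**What the plan says.** **Definitions (SAP 2.1.1).** The on-treatment period starts at first dose. It ends at "30 days after the last treatment visit (Day 183) if not missing or the date of last treatment visit attended" for drop-outs, or at death during the treatment epoch. A treatment-emergent adverse event must fall within this period. EoT "refers to the last date of the on-treatment period as defined above". The section also defines a date of last administration, which "refers to the date on which the study drug/treatment was given for the last time in the cohort of the study", but does not use it to close the on-treatment period.

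**Primary endpoint.** SAP 2.5.1 introduces its formula with "It will be calculated as" and gives FVC%p at EoT minus FVC%p at baseline. SAP Table 1-1 states the endpoint as "Change from baseline to end of treatment epoch (26 weeks of treatment) in Forced Vital Capacity (FVC) expressed in percent predicted". The summary measure in SAP 2.5.2 is the difference "between active and placebo at week 26 derived from the Bayesian statistical model". Protocol Table 8-1 labels the Day 183 ±5 visit as EOT.

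**Other safety windows.**
- SAP Table 5-2 ends the on-treatment period at the last treatment date plus 30 days, no later than death, cut-off or withdrawal of consent. Its note confines these imputations to time-to and duration analyses.
- SAP 2.6.1.2 restricts safety summaries to on-treatment data, but runs adverse event tables to the close of safety follow-up. Its wording on treatment-emergent events gives no end date.
- Protocol 17.1.10 sets Cohort 1 follow-up at 30 (+14) days after the last administration.

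**Visits after stopping.** Under protocol 9.1.1, participants who stop drug still attend all remaining visits, including Day 183. Under protocol 9.1.2, those who leave the study have an early EoT visit within 4 weeks.

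**The concern.** Two different needs share one definition. The efficacy endpoint needs a visit at week 26. The safety analysis needs a window that follows exposure. By setting EoT to the end of the safety window, 2.1.1 moves the date in the 2.5.1 formula past the visit it is meant to describe.

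On the safety side, the period is tied to visit attendance and not to dosing. A participant who stops drug early but keeps attending stays on-treatment until a month after Day 183. For a participant who leaves the study, the sentence does not say whether the 30 days also apply to the last visit attended. Table 5-2 gives the same named period another end date, and 2.6.1.2 uses a third limit for adverse event tables.

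This end date decides which adverse events are treatment-emergent, which data enter the safety summaries, and which laboratory value is taken as the worst on-treatment value in the shift tables. Two programmers following the SAP could produce different counts.

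**Working it through.** **Inputs.** Study day = date − Day 1 + 1 (SAP 2.1.1). Treatment period 26 weeks, Day 1 to Day 183 (SAP 1.1). EOT visit Day 183 ±5 and treatment visits at Days 29, 57, 85, 113, 141 and 183 (protocol Table 8-1). The end-date rules are those of SAP 2.1.1, SAP Table 5-2 and protocol 17.1.10. Two assumptions: the last treatment date in Table 5-2 means the last dose, and a completer takes the last dose on Day 183.

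**1. The plan's own figure.** 26 × 7 + 1 = 183, which matches.

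**2. Literal EoT when Day 183 is attended.** 183 + 30 = Day 213, and (213 − 1)/7 = 30.3 weeks, against (183 − 1)/7 = 26.0. With the visit window, 178 + 30 = Day 208 (29.6 weeks) to 188 + 30 = Day 218 (31.0 weeks).

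**3. Drug stopped on day d, Day 183 attended.** SAP 2.1.1 ends on Day 213 and Table 5-2 on d + 30, so the excess is 213 − (d + 30) = 183 − d (±5 with the visit window). The last column counts nominal visits later than d + 30 and up to Day 183. Vital signs are marked at each of these.

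| Last dose (day) | End, SAP 2.1.1 | End, Table 5-2 | Excess (days) | Extra visits counted |
|---|---|---|---|---|
| 29 | 213 | 59 | 154 | 4 |
| 57 | 213 | 87 | 126 | 3 |
| 85 | 213 | 115 | 98 | 2 |
| 113 | 213 | 143 | 70 | 1 |
| 141 | 213 | 171 | 42 | 1 |
| 183 | 213 | 213 | 0 | 0 |

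This result does not depend on how the drop-out clause is read, because the Day 183 visit is not missing.

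**4. Study leaver, last dose d, early EoT visit at d + k, with k from 0 to 28.**
- If the 30 days do not apply to the drop-out clause, 2.1.1 ends at d + k. That is 30 − k days short of d + 30: from 30 days down to 2.
- If they do apply, 2.1.1 ends at d + k + 30, which is 0 to 28 days beyond d + 30.

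**5. Completer, last dose on Day 183.** SAP 2.1.1 and Table 5-2 both end on Day 213. The follow-up visit falls between 183 + 30 = Day 213 and 183 + 44 = Day 227. Days 214 to 227, up to 14 days, are inside the adverse event table window and outside the on-treatment period.

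**The case against.** The strongest reply is that the EoT wording is a drafting slip that changes no planned analysis. Apart from its definition, EoT enters only the one-line formula in 2.5.1. The primary analysis is a random-slope model read at week 26, the secondary models also refer to 26 weeks, and a programmer is unlikely to be misled. This stands as far as the primary result goes: no shift is shown. The formula is still wrong as written, and the text as read does not show whether spirometry is scheduled near Day 213.

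Second, the Table 5-2 rule serves only time-to and duration analyses, and it agrees with 2.1.1 for completers. Both points are correct. The conflict between those two rules concerns participants who stop drug early or leave, and the documents give no count of them. One named period still has two end dates.

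Third, counting events to a month after Day 183 in people off drug can be defended as an inclusive safety window, and protocol 10.1.1 sets how long events are monitored, not how they are analysed. That is fair. Its minimum is also 30 days or 5 half-lives, whichever is longer, so it supports the last-dose anchor and not a fixed length. But the SAP does not present the long window as a deliberate choice, and on one reading the same sentence gives study leavers no days after their last visit.

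Fourth, the sentence on adverse event tables in 2.6.1.2 can be read as an exception to the on-treatment limit, and at the nominal 30-day follow-up there is no gap for completers. On that reading, 2.1.1 still excludes from the treatment-emergent definition events that the table window admits whenever follow-up uses its 14-day allowance.

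Finally, the laboratory rows of the visit schedule are not readable in the text available, so only vital-sign visits were counted. The rule would treat any laboratory values collected in that time in the same way.

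**Conclusion.** The point holds and should be fixed. Read literally, the primary endpoint formula refers to Day 213 (Day 208 to 218) for anyone who attends Day 183, 30 days beyond the 26-week visit. The decision rule and the secondary models stay at week 26, so this is a wrong derivation rule with no demonstrated effect on the primary result.

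The larger consequence is for safety. For participants who stop drug but attend Day 183, the 2.1.1 period outlasts the Table 5-2 period by, for example, 126 days (last dose Day 57) or 70 days (last dose Day 113), and takes in three vital-sign visits or one that the dose-anchored rule would leave out. For study leavers the period is 2 to 30 days short of last dose plus 30, or 0 to 28 days beyond it, depending on how the sentence is read. For completers the only discrepancy is with the adverse event table window, at most 14 days.

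These are differences in dates for example participants under the two assumptions stated above. No actual miscount and no imbalance between arms is claimed.

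**What to change.** - In SAP 2.1.1, define EoT for efficacy as the scheduled Day 183 (week 26) visit, separate from the safety window.
- In SAP 2.5.1, state the endpoint as the week-26 change in FVC%p estimated by the 2.5.2 model.
- Use one on-treatment end date for every participant in both 2.1.1 and Table 5-2. The SAP's own rule, last treatment date plus 30 days with its caps, is suitable and shares the last-dose anchor of protocol 10.1.1. State that the last treatment date means the date of last administration.
- In SAP 2.6.1.2, say whether treatment-emergent tables stop at that date or continue to the end of safety follow-up, and word the treatment-emergent definition to match.
- List separately the adverse events that start after the window in participants who stop drug but remain in the study.

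The cost is wording before database lock. Visit, dosing and event dates are already collected. The one drawback is that a dose-anchored window counts fewer late events as on-treatment in those who stop drug and stay on; the separate listing keeps them visible.
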